3.5.2. Laboratory Data

Safety laboratory tests will be performed as described in the protocol.

PFIZER GENERAL BUSINESS

To determine if there are any abnormalities of potential clinical concern, the hematology, chemistry and urinalysis safety tests will be assessed against the criteria specified in the CaPS. The assessment will take into account whether each participant's baseline test result is within or outside the laboratory reference range for the particular laboratory parameter.

Baseline will be the last pre-dose measurement collected on Day -1.

3.5.3. Vital Signs

Supine systolic and diastolic blood pressure and pulse rate (PR) will be taken at all time points listed in the Schedule of Activities given in the protocol. The last pre-dose measurement at Day 1 will be used as the baseline.

The maximum decrease and increase from baseline over all measurements taken postdose for supine systolic and diastolic blood pressures will be determined. The maximum increase from baseline will be calculated by first subtracting the baseline value from each postdose measurement to give the change from baseline. The maximum of these values over the entire study will then be selected, except in the case where a participant does not show an increase. In such an instance, the minimum decrease should be taken. Similarly, the maximum decrease from baseline will be determined by selecting the minimum value of the change from baseline. In cases where a subject does not show a decrease, the minimum increase should be taken.

3.5.4. Electrocardiograms

Standard 12-lead ECGs will be taken at all time points listed in the Schedule of Activities given in the protocol. The last pre-dose measurement at Day 1 will be used as the baseline.

The QT, QTc, PR, QRS and heart rate will be recorded at each assessment time.

If not supplied, QTcF will be derived using Fridericia's heart rate correction formula:

$$\text{QTcF} = \text{QT} / (\text{RR})^{1/3} \text{ where RR} = 60/\text{HR} \text{ (if not provided)}$$

The maximum absolute value (postdose) and the maximum increase from baseline will be determined over all measurements taken postdose for QTcF, PR and QRS.

The maximum increase from baseline will be calculated by first subtracting the baseline value from each postdose measurement to give the change from baseline. The maximum of these values over the respective period will then be selected, except in the case where a participant does not show an increase. In such an instance, the minimum decrease should be taken.

[figure not shown]
4. ANALYSIS SETS (POPULATIONS FOR ANALYSIS)

Data for all participants will be assessed to determine if participants meet the criteria for inclusion in each analysis population prior to unblinding and releasing the database and classifications will be documented per standard operating procedures.

Participant Analysis Set	Description
Enrolled/Randomly assigned to study intervention	"Enrolled" means a participant's, or their legally authorized representative's, agreement to participate in a clinical study following completion of the informed consent process. Potential participants who are screened for the purpose of determining eligibility for the study, but do not participate in the study, are not considered enrolled, unless otherwise specified by the protocol. A participant will be considered enrolled if the informed consent is not withdrawn prior to participating in any study activity after screening.
Safety Analysis Set	All participants randomly assigned to study intervention and who take at least 1 dose of study intervention. Participants will be analyzed according to the product they actually received.
PK concentration	All participants randomly assigned to study intervention who received at least 1 dose of study intervention and in whom at least 1 serum sample concentration value of PF-06823859 is reported.
PK parameter	All participants randomly assigned to study intervention who received at least 1 dose of study intervention and who have at least 1 of the PK parameters of PF-06823859 of interest calculated.
Immunogenicity	All participants randomly assigned to study intervention who received at least 1 dose of study intervention with at least one post-treatment anti-drug (PF-06823859) antibody determination.

If a participant receives a treatment that is not consistent with the treatment they are randomly assigned to, then the participant will be reported under the treatment that the participant actually received for all PK, immunogenicity and safety analyses, where applicable.

PFIZER GENERAL BUSINESS

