6.3.2. Breaking the Blind

The method for breaking the blind in this study will be manual. A sealed envelope that contains the study intervention assignment(s) for each participant will be provided to the investigator. The sealed envelope will be retained by the investigator (or representative) in a secured area. In case of an emergency, the investigator has the sole responsibility for determining if unblinding of a participant's treatment assignment is warranted. Participant safety must always be the first consideration in making such a determination. If the investigator decides that unblinding is warranted, the investigator should make every effort to contact the sponsor prior to unblinding a participant's treatment assignment unless this could delay further management of the participant. If a participant's treatment assignment is unblinded, the sponsor must be notified within 24 hours after breaking the blind. When the blinding code is broken, the reason must be fully documented and entered on the CRF.

Once the study is complete, all envelopes (sealed and opened) must be inventoried and retained until authorization for destruction has been provided.

Blood specimens will be obtained from all participants for PK analysis to maintain the study blind at the investigator site. Only the investigator site staff and blinded study monitor, if assigned, will be blinded to study treatment. Other Pfizer personnel will be unblinded to participant treatments in order to permit real-time interpretation of the safety and PK data. The blinded study monitor, if assigned, will remain blinded to treatment until all monitoring for the study has been completed. Specimens from participants randomized to placebo will not be routinely analyzed. To minimize the potential for bias, treatment randomization information will be kept confidential by Pfizer unblinded personnel and will not be released to the blinded investigator or blinded investigator site personnel until the study database has been locked or the investigator requests unblinding for safety reasons.

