The PK samples must be processed and shipped as indicated in the instructions provided to the investigator site to maintain sample integrity. Any deviations from the PK sample handling procedure (eg, sample collection and processing steps, interim storage or shipping conditions), including any actions taken, must be documented and reported to the sponsor.

On a case-by-case basis, the sponsor may make a determination as to whether sample integrity has been compromised.

Drug concentration information that would unblind the study will not be reported to investigator sites or blinded personnel until the study has been unblinded.

Any changes in the timing or addition of time points for any planned study assessments must be documented and approved by the relevant study team member and then archived in the sponsor and site study files, but will not constitute a protocol amendment. The IRB/EC will be informed of any safety issues that require alteration of the safety monitoring scheme or amendment of the ICD.

CCI

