5. GENERAL METHODOLOGY AND CONVENTIONS

This is a double-blind and sponsor-open study. As this is a sponsor-open study, the sponsor may conduct unblinded reviews of the data during the course of the study for the purpose of safety assessment, facilitating PK/PD modeling, and/or supporting clinical development. Treatment randomization information will be kept confidential by Pfizer unblinded personnel and will not be released to the blinded investigator or blinded investigator site personnel until the study database has been locked or the investigator requests unblinding for safety reasons. Final analysis will follow the official database release.

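### Can the analysis sets be fixed before unblinding, and infusion reactions be grouped blind, in a sponsor-open trial where PK-set membership reveals treatment?

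*SAP*

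**What the plan says.** SAP section 4 has all participants' data assessed "to determine if participants meet the criteria for inclusion in each analysis population prior to unblinding and releasing the database", and adds that the classifications are documented under standard operating procedures. Of the sets listed there, the PK concentration set takes dosed participants "in whom at least 1 serum sample concentration value of PF-06823859 is reported", and the PK parameter set takes those "who have at least 1 of the PK parameters of PF-06823859 of interest calculated".

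The blinding rules are in Protocol section 6.3.2. The blind is confined to two groups: "Only the investigator site staff and blinded study monitor, if assigned, will be blinded to study treatment". The remaining sponsor staff know the assignments, and the reason is given in the same place: "Other Pfizer personnel will be unblinded to participant treatments in order to permit real-time interpretation of the safety and PK data". On the assay of placebo samples the section says: "Specimens from participants randomized to placebo will not be routinely analyzed". Protocol section 8.4 adds a rule on what blinded people may be told: "Drug concentration information that would unblind the study will not be reported to investigator sites or blinded personnel until the study has been unblinded". SAP section 5 says that randomization information "will not be released to the blinded investigator or blinded investigator site personnel until the study database has been locked", or until the investigator asks for unblinding for safety reasons. It also allows the sponsor unblinded reviews during the study.

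SAP section 6.1.1 selects the adverse events that count as IRR by a medical review that is to be blind and done before database release. It names no role for the reviewer. IRR is part of the primary endpoint (SAP section 3.1).

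**The concern.** Two steps in the SAP read like text for a trial in which the sponsor is blinded, and this trial is sponsor-open.

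First, if placebo samples are not assayed, a placebo participant has no concentration to report and no parameter to calculate. Sorting participants into the PK sets then sorts them by arm, and the cohort gives the dose. A person who was blind before doing this would not be blind afterwards, so the claim that every set is fixed before unblinding seems to contradict the set definitions.

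Second, grouping events as IRR is a judgement. Viral infections are defined in the same section by a project list of targeted events, but IRR has no such list, so blinding is the main safeguard stated there. If unblinded sponsor physicians did the review, calling it blind would be wrong.

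What is at stake is whether two statements about bias control are accurate. With 2 placebo participants, reclassifying one participant for IRR moves the placebo rate by 1/2 = 50 percentage points. In an active group of 5 it moves the rate by 1/5 = 20 points.

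**Working it through.** **Planned numbers.** Protocol Table 1 and SAP Table 2 give 5 active and 1 placebo in each of 2 cohorts: 2 × (5 + 1) = 12, of whom 10 are active and 2 placebo. This matches the total in Protocol section 9.5, which says that the number has no statistical basis.

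**What PK-set membership discloses.**
- Before looking, a blinded reader who knows the cohort faces 6 × 6 = 36 possible allocations. The chance that a given participant is active is 5/6 = 0.83.
- If no placebo sample is assayed and all 10 active participants have a reported value, 10 are in the set and 2 are out. One allocation remains.

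The documents give no rates for departures from this pattern, so the following are assumptions. Let *r* be the chance that a placebo participant has a reported concentration and *q* the chance that an active participant has none.

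P(active | in set) = (5/6)(1 − q) / [(5/6)(1 − q) + (1/6)r]

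P(placebo | not in set) = (1/6)(1 − r) / [(1/6)(1 − r) + (5/6)q]

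| r | q | P(active, in set) | P(placebo, not in set) |
|---|---|---|---|
| 0 | 0 | 1.00 | 1.00 |
| 0 | 0.02 | 1.00 | 0.91 |
| 0 | 0.05 | 1.00 | 0.80 |
| 0 | 0.10 | 1.00 | 0.67 |
| 0.05 | 0 | 0.99 | 1.00 |
| 0.20 | 0 | 0.96 | 1.00 |
| 1 | 0 | 0.83 | none outside |

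Membership of the concentration set stops being informative only if placebo samples are all assayed and reported. The premise that PK-set membership reveals treatment therefore holds under routine handling.

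**Whether that creates a contradiction.** The passages have to be read together.
- The SAP 4 sentence says when the classification is done. It does not say that a blinded person does it.
- Protocol section 8.4 speaks of the study having been unblinded as an event that governs what sites and blinded personnel may receive. SAP section 5 ties release of treatment information to the site to database lock. Read in the same sense, SAP 4 puts the classification before that release.
- Protocol section 6.3.2 supplies sponsor staff who are already unblinded and who may see concentrations. They can classify the PK sets at that time without breaking any rule.
- The 36-to-1 reduction matters only if a blinded person receives PK-set membership. Protocol section 8.4 and the confidentiality rules in Protocol section 6.3.2 and SAP section 5 are written to prevent that.
- The enrolled and safety sets need consent, randomization and dosing facts only. They disclose nothing about arm and can be settled by anyone.

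**Whether the IRR review can be carried out as written.** SAP section 6.1.1 requires a blind review. Protocol section 6.3.1 keeps investigators blinded throughout, so a qualified blinded role exists. Staff who prepare and dispense the product are unblinded (Protocol sections 6.1 and 6.2.1) and would not qualify. IRR selection does not use PK-set membership, so the first point does not carry over to the second.

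**The case for a change.** The strongest case for a change is that the milder reading of SAP 4 removes the conflict only by emptying the sentence. If unblinding means release to the site, then fixing the sets beforehand says nothing about whether those who classify know the treatments, and most sponsor staff do. For IRR, the SAP's silence leaves room for sponsor physicians to do the review. Removing treatment codes from their listings would not restore a blind they no longer have. Version 2 of the SAP was issued partly to clarify the IRR definition and still left the reviewer open.

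Part of this stands. The word unblinding is ambiguous for the two PK sets, and a sentence naming the IRR reviewer's role and blinding status would make the record easier to audit.

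The rest does not support a change. The criteria for the sets are factual (a value is reported or not, a parameter is calculated or not), so knowing the arm gives little scope to steer membership. Reassigning classification as a whole to unblinded staff would be worse than the present text, because it would cover the enrolled and safety sets without need. For IRR, a review by unblinded staff would depart from the SAP; it would not be a consequence of following it. Assigning the review to a site physician has its own cost, since that person may be judging events recorded at the same site. The operating procedures that SAP section 4 cites are not available here and may already say who classifies and with what access.

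**Conclusion.** No change follows. The PK-set point is an ambiguity of wording that the blinding rules elsewhere resolve. The IRR point is an operational detail that a study team following the plan would fill sensibly, by giving the review to someone who is blinded.

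The consequence is small. The trial tests no hypotheses and has no decision rules (Protocol section 9.1, SAP section 5.1). Adverse events are listed as well as summarized (SAP section 6.1.1). Intensity and causality are assigned by the investigator (Protocol Appendix 3), who stays blinded. No miscount of IRR is shown, and no set, estimate or table is shown to change.

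This rests on three assumptions: that unblinding in SAP 4 means release of treatment information around database lock, that concentration data and PK-set membership are withheld from blinded roles as the protocol requires, and that the IRR reviewer is in fact blinded. If unblinded sponsor staff did the review, the study report should not describe it as blind.

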5. GENERAL METHODOLOGY AND CONVENTIONS

This is a double-blind and sponsor-open study. As this is a sponsor-open study, the sponsor may conduct unblinded reviews of the data during the course of the study for the purpose of safety assessment, facilitating PK/PD modeling, and/or supporting clinical development. Treatment randomization information will be kept confidential by Pfizer unblinded personnel and will not be released to the blinded investigator or blinded investigator site personnel until the study database has been locked or the investigator requests unblinding for safety reasons. Final analysis will follow the official database release.

5.1. Hypotheses and Decision Rules

There are no statistical hypotheses or decision rules.

5.2. General Methods

All data will be descriptively summarized by treatment (PF-06823859 300 mg, PF-06823859 900 mg, and placebo). Data from placebo in Cohort 1 and Cohort 2 will be pooled for all analyses.

5.2.1. Analyses for Binary Endpoints

Number and percentage of participants in each category will be used to summarize the binary endpoints, if not otherwise specified.

5.2.2. Analyses for Continuous Endpoints

The summary statistics n, arithmetic mean, median, standard deviation (SD), minimum and maximum will be used to summarize the continuous endpoints, if not otherwise specified.

5.2.3. Analyses for Categorical Endpoints

Number and percentage of participants in each category will be used to summarize the categorical endpoints, if not otherwise specified.

5.3. Methods to Manage Missing Data

5.3.1. Safety Data

Missing values in standard summaries of AEs, laboratory data, vital signs, and ECGs will be imputed according to CaPS.

5.3.2. Pharmacokinetic Data

Concentrations below the Limit of Quantification

In all data presentations (except listings), concentrations below the limit of quantification (BLQ) will be set to zero. (In listings BLQ values will be reported as “<LLQ”, where LLQ will be replaced with the value for the lower limit of quantification.)

PFIZER GENERAL BUSINESS

Deviations, Missing Concentrations and Anomalous Values

In summary tables, plots of mean profiles and plots of median profiles, summary statistics will be calculated setting concentrations to missing if one of the following cases is true:

- A concentration has been collected as ND (i.e., not done) or NS (i.e., no sample);
- A deviation in sampling time is of sufficient concern or a concentration has been flagged anomalous by the pharmacokineticist.

Note that summary statistics will not be presented at a particular time point if more than 50% (>50%) of the data are missing.

Pharmacokinetic Parameters

Actual PK sampling times will be used in the derivation of PK parameters.

If a PK parameter cannot be derived from a participant's concentration data, the parameter will be coded as NC (i.e., not calculated). (Note that NC values will not be generated beyond the day that a participant discontinues.)

In summary tables, statistics will be calculated by setting NC values to missing; and statistics will be presented for a particular dose with ≥ 3 evaluable.

If an individual participant has a known biased estimate of a PK parameter (due for example to an unexpected event such as known loss of drug during IV administration), this will be footnoted in summary tables and will not be included in the calculation of summary statistics.

6. ANALYSES AND SUMMARIES

6.1. Primary Endpoint(s)

[figure not shown]
The primary endpoints will be listed and summarized by treatment (PF-06823859 300 mg, PF-06823859 900 mg, and placebo) in accordance with CaPS, where the resulting data presentations will consist of participants from the safety analysis set. Data from placebo in Cohort 1 and Cohort 2 will be pooled.

6.1.1. Adverse Events

Adverse events will be listed and summarized in accordance with CaPS.

IRR (Infusion Related Reaction) will include adverse events potentially related to infusion related reaction and will be determined by blind medical review prior to the database release. The incidence and severity of IRR will be summarized by treatment group. The incidence and severity of IRR will also be summarized by system organ class (SOC) and preferred term

PFIZER GENERAL BUSINESS

(PT) by severity. Separate tables will be prepared by all causalities and treatment-related for these summaries.

The incidence and clinical significance of infusion site reaction will be summarized by treatment group. The incidence and severity of infusion symptoms will also be listed and summarized by treatment group. The detail on infusion site reaction collected in CRF will also be listed.

Viral infections will include adverse events which are specified by the latest targeted medical events (TMEs) related to infections for C025 project. The incidence and severity of viral infections will be summarized by treatment group. The incidence and severity of viral infections will also be summarized by SOC and PT by severity. Separate tables will be prepared by all causalities and treatment-related for these summaries.

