2.2.2.1. Safety

Data from Study C0251001 suggests that PF-06823859 was generally well tolerated and safe when given up to 2000 mg as single IV dose and up to 1800 mg given 600 mg IV Q2W × 3. The most common AE was upper respiratory tract infection, likely due to viral infection. No serious AE or death occurred during the study.

During the SAD period, all TEAEs reported were mild in severity. During the MAD period, while the majority of the TEAEs were mild in severity, 4 TEAEs were moderate in severity: 2 TEAEs (abdominal pain upper and headache) in the placebo SC × 3 doses treatment group, 1 TEAE (upper respiratory tract infection) in the PF-06823859 300 mg SC × 3 doses treatment group and 1 TEAE (sinusitis) in the PF-06823859 600 mg IV (Q4W) × 2 doses treatment group, none of which were considered by the investigator as treatment related.

One participant experienced a mild localized erythema with induration and tenderness after each of the 100 mg SC dosing with PF-06823859 administered Q2W for a total of 3 doses, but no signs or symptoms of a systemic reaction. These local reactions resolved without further intervention within a few days. This participant also had treatment-induced ADA, which had returned to baseline at the time of discharge ([Section 2.2.2.3](#)).

Overall, there was no apparent difference in the total rate of AEs between the participants treated with PF-06823859 compared to placebo and no apparent dose relationship with the doses of PF-06823859. However, the rate of mild upper respiratory tract infection appears to be higher in participants treated with PF-06823859.

There were no clinically significant observations in ECG, vital signs or laboratory abnormalities.

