8.2.8. Viral Surveillance

Blood samples for possible analysis of CMV, EBV, HSV-1, HSV-2, VZV and HHV6 will be collected according to the times outlined in the [SoA](#).

Note: Due to long turnaround time, the retrospective nature of these labs might make their reporting time quite delayed.

In addition to time points specified in the [SoA](#), a blood sample for viral surveillance sample may also be taken at the time of an AE, as clinically appropriate.

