1. VERSION HISTORY

Table 1. Summary of Changes

Version/ Date	Associated Protocol Amendment	Rationale	Specific Changes
1 21JUL2021	Original 26MAY2021 Amendment 1 09JUL2021	N/A	N/A
2 14APR2022	N/A	Some clarifications were added.	Section 6.1.1: Added clarification on the definition of IRR and viral infections. Sections 6.1.3 and 6.1.4: The categorical classes for vital signs and ECGs were specified in Appendix 1. Overall: Minor edits for the description maintenance.

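### Does the viral infections part of the primary safety endpoint need a frozen term list and its own surveillance table?

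*SAP*

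**What the plan says.** Protocol section 3 and SAP section 3.1 make the primary endpoint a set of safety assessments. Viral infections are named inside the adverse event component, alongside infusion related reactions (IRR) and infusion sites. Laboratory tests are a separate component.

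SAP section 6.1.1 first commits to listing and summarising adverse events in general. It then sets the rule for the viral subset: "Viral infections will include adverse events which are specified by the latest targeted medical events (TMEs) related to infections for C025 project". That subset is tabulated by treatment, and by system organ class and preferred term with severity, for all causalities and for treatment-related events. For IRR the same section adds a safeguard: membership "will be determined by blind medical review prior to the database release". The SAP's version history shows that both definitions came in with version 2: "Section 6.1.1: Added clarification on the definition of IRR and viral infections".

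On laboratory data, SAP section 3.5.2 says that "the hematology, chemistry and urinalysis safety tests will be assessed against the criteria specified in the CaPS" and sets the baseline at Day -1. SAP section 6.1.2 says laboratory data will be listed and summarised by treatment. Protocol section 8.2.8 collects blood for possible analysis of six viruses and warns: "Due to long turnaround time, the retrospective nature of these labs might make their reporting time quite delayed".

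**The concern.** Four features look troubling together.

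- **The list is not fixed.** It is whatever is current at analysis, with no terms, version or freeze date. Under Protocol section 6.3.2, "Other Pfizer personnel will be unblinded to participant treatments in order to permit real-time interpretation of the safety and PK data". IRR gets a blind review and viral infections do not.
- **Label and rule differ.** The endpoint says viral and the list says infections. Non-viral events could enter, and respiratory infections of unspecified cause might not. Protocol section 2.2.2.1 reports from the completed Study C0251001: "The most common AE was upper respiratory tract infection, likely due to viral infection". It adds: "However, the rate of mild upper respiratory tract infection appears to be higher in participants treated with PF-06823859".
- **Only adverse events count.** An asymptomatic positive for CMV, VZV, EBV, HHV6 or HSV-1/2 that nobody judges clinically relevant stays outside the component.
- **The SAP never names the surveillance results**, and its check for abnormalities of potential concern covers three other laboratory groups.

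Protocol section 2.3 identifies greater susceptibility to viral infection as a potential risk of blocking IFN-beta. If the plan could lose such events, the primary safety result would be weaker on a risk the monitoring was designed to watch.

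**Working it through.** The documents give no event rate, power or alpha for this component, so there is no planned figure to reproduce. The check has two parts: how far the list can move the dedicated table, and whether an event or result left off it is lost.

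**Inputs.** Protocol section 9.5 and Table 1: two cohorts of 5 active + 1 placebo, so 2 × (5 + 1) = 12, with 10 active and 2 placebo, as stated. Protocol section 9.1 and SAP section 5.1: no hypotheses and no decision rules.

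**Effect of one participant.** 1/5 = 20 percentage points in a dose group; 1/2 = 50 points in pooled placebo. These steps apply to any event in a trial of this size, not only to this list.

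**Effect of list coverage.** Let p be the true proportion of participants with a viral infection event and s the share of such events whose term is on the list. Neither is in the documents; both are assumptions. The chance that the dedicated table shows at least one case among 10 active participants is 1 − (1 − p·s)^10:

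| p | s = 1 | s = 0.5 | s = 0 |
|---|---|---|---|
| 10% | 0.651 | 0.401 | 0 |
| 20% | 0.893 | 0.651 | 0 |
| 40% | 0.994 | 0.893 | 0 |

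For example, p = 20% and s = 0.5 gives 1 − 0.9^10 = 0.651. Coverage can therefore decide what that one table shows.

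**Following an upper respiratory infection through the plan.** The investigator, who is blinded, records it as an adverse event. It appears in the general listing and summary whatever the list contains. If it is on the list, it also appears in the viral tables under its own preferred term. If it is not, a reader comparing the two tables can see that. The general tables do not depend on s.

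**Following a surveillance result.** Protocol Appendix 2, Table 3 places the six viruses among the required safety laboratory assessments. SAP section 6.1.2 lists and summarises laboratory data without restricting the tests. The sentence in SAP section 3.5.2 on hematology, chemistry and urinalysis limits only the check against criteria of potential concern; it does not limit what is listed. Protocol section 8.2.6 and Appendix 2 also require the investigator to review laboratory reports and record clinically relevant changes as adverse events. A late result is still a reportable result.

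**Baseline.** The Schedule of Activities row for viral surveillance appears to show a screening sample and none on Day -1 (the table layout is broken). The Day -1 laboratory baseline therefore does not fit. SAP section 3.4 gives a general default that allows the last measurement from screening, and screening is the only pre-dose value an analyst would have.

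**The case for a change.** The strongest case for a change is that this is a named part of the primary endpoint, and both Protocol section 9 and SAP section 2 reserve major changes in primary endpoint definitions for a protocol amendment. A list that tracks its latest version can change what is counted with no visible change to either document. The authors knew how to fix membership blind, because they did so for IRR in the same section and the same SAP version. The remedy would be cheap: a dated list and one table.

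Part of this stands. The list version is uncited, no blind freeze is stated, whether pathogen-unspecified respiratory infections count cannot be read from the documents, and no rule defines a newly positive surveillance result.

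The rest does not carry. The list belongs to the C025 project rather than to this study, and the documents do not say who maintains it, so tailoring to these data is conjecture. The respiratory signal comes from the earlier study, and since the list is not in the documents, its omission of that term is a guess. Counting adverse events only follows from the endpoint's own wording, which puts viral infections within adverse events and laboratory tests beside them. Asking for a strictly viral list and also for respiratory infections of unknown cause pulls in opposite directions; either choice is a preference. A table of new positives would also need an assay and a positivity rule that the documents do not give, for samples whose analysis is only possible.

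**Conclusion.** No change to the plan follows. These are missing details that analysts fill sensibly: they would cite the list version used, show the terms counted, and present any surveillance results analysed against screening. The exposure is confined to the dedicated viral infections tables and the layout of the surveillance data. Within those tables the 20- and 50-point steps are real, but they feed no test, threshold or decision in a descriptive study of 12 participants. The overall adverse event tables do not move at all.

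This rests on two assumptions: that the sponsor's standard adverse event summaries cover all events, as SAP section 6.1.1 indicates, and that the tests in Protocol Table 3 are treated as laboratory data under SAP section 6.1.2. A decision rule tied to the viral infections count would change the conclusion; the plan has none.
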